Major depressive disorder (MDD) is a recurrent and chronic mood disorder that affects 14% of the adult population during their lifetime. Current treatment options are partially effective and the neurobiology of MDD is largely unknown. Recent evidence points to an important role of brain-body communication in the integration of mood and therefore in depression. Information travelling from the body to the brain through the dorsal horns in the spinal cord is essential to provide consciousness of emotional experience in a process called interoceptive awareness. This information is then used by the brain to adjust bodily function through hypothalamic and autonomic outputs. Increased sympathetic activity and somatic symptoms have been documented in MDD and suggest disturbed brain-body communication. Spinal cord stimulation (SCS) has been used in the past to decrease sympathetic activity and modulate spinal input to the brain. Indirect evidence suggests that SCS might have antidepressant effects. Transcutaneous spinal direct current stimulation(tsDCS) devices represent an effective, non-invasive, low cost alternative to surgically implanted SCS devices. We believe that extant data support our overarching HYPOTHESIS that an altered sensory input to the brain through the dorsal horns of the spinal cord contributes to the pathophysiology of depressive symptoms and that tsDCS will be effective and safe in treating MDD by decreasing sympathetic activity and restoring metabolic function. Thus, we aim to 1) determine the efficacy and safety of tsDCS in adult patients with MDD and 2) investigate interoceptive awareness, somatic symptoms, autonomic and metabolic regulation as potential mediators of antidepressant response to tsDCS. We predict that 1) Active tsDCS treatment will result in a greater decrease in depressive symptom severity compared to Sham tsDCS in adult patients with MDD, 2) active tsDCS will be safe and well tolerated in adult patients with MDD and 3) change in interoceptive awareness, somatic symptoms, and autonomic and metabolic parameters will be associated with change in depressive symptom severity. To accomplish these aims, we will conduct an 8-week, double blinded, randomized, sham controlled, parallel group, pilot clinical trial study design. A total of 20 adult antidepressant-free MDD patients will be randomized to receive Active (n=10) or Sham (n=10) tsDCS protocols for 8 weeks in a 1:1 ratio. As an initial test of our hypothesis, we will combine the use of a tsDCS device, psychometric instruments to diagnose MDD (M.I.N.I.), and measures of depressive symptom severity (MADRS and PHQ-9), somatic symptoms (4DSQ), interoceptive awareness (MAIA), autonomic function (blood pressure, heart rate), and potential metabolic markers (cortisol, LCn-3 fatty acids, adiponectin, leptin, insulin and fibroblast growth factor-21) known to be regulated by sympathetic activity as predictors of response. This will be the first pilot study to evaluate the potential antidepressant effects of tsDCS in adult patients diagnosed with MDD. It is anticipated that the results of this pilot clinical trial will provide preliminary data in support of a larger future trial that will additionally incorporate neuroimaging to investigate central mechanisms.

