Specific Aim 2: To investigate interoceptive awareness, anxiety and somatic symptoms, autonomic and metabolic regulation as potential mediators of antidepressant response to tsDCS. Prediction 3: Change in interoceptive awareness, somatic symptoms, and autonomic and metabolic parameters will be associated with change in depressive symptom severity. Prediction 4: Active tsDCS treatment will result in a greater decrease in depressive symptom sub-components, interoceptive awareness, anxiety and somatic symptoms, autonomic and metabolic parameters.

To accomplish these aims, we will randomize 20 adult antidepressant-free MDD patients to active (n=10) or sham (n=10) tsDCS protocols for 8 weeks in a double blind 1:1 ratio. We will evaluate clinical, autonomic, and metabolic variables that may be involved in the proposed mechanism as possible mediators of antidepressant response. This will be the first 8-week, double blinded, randomized, sham controlled, parallel group pilot clinical trial to evaluate the efficacy and safety of tsDCS in adult patients with MDD. It is anticipated that the results of this pilot trial will provide preliminary data in support of a larger future trial that will additionally incorporate neuroimaging to investigate central mechanisms.

B. BACKGROUND AND SIGNIFICANCE:

B.1 Public Health Significance:

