D.1.2. Spinal cord stimulator and stimulation protocol. The 2x2 Soterix® Medical transcutaneous spinal direct current stimulator model 0707-A device will be used. This is a tsDCS available only for investigational use, with which [name] has extensive experience and will provide appropriate training to the study team. This device will be appropriately labeled as an “Investigational Device. Federal (Law) limits device to investigational use”. The device will be kept in a secured area inside the LCOH Research Institute and will be made available only to trained personnel of the study team. This device allows anodal stimulation to be delivered at 2.5mA per 20-minute session or sham session consisting of short pulses (of the desired intensity) at the beginning and end of the sessions. This protocol of anodal stimulation has been reported to be effective in inhibiting ascending pathways with a lasting effect, to be safe and well under the threshold for tissue damage (77, 79). If stimulation intensity (in active or sham protocols) is not tolerable at 2.5mA, the clinician may decide to decrease intensity to 2.0 mA or 1.5 mA. If 1.5 mA stimulation intensity is not tolerated, the subject may be withdrawn from the study. If subject has tolerated a stimulation intensity of less than 2.5mA, the study clinician may attempt to increase the dose to 2.0mA or 2.5mA when considered clinically appropriate. An anode electrode (5x10cm) will be placed at the level of the 10th vertebrae spinal process. At this level, the current is expected to spread longitudinally through the spinal cord up to three additional vertebral levels (96). The cathode (5x7cm) electrode will be placed on the right shoulder over the deltoid area (78, 79, 97). Participants will be scheduled to receive sham or active tsDCS sessions three times/week. Subjects will be randomized in a 1:1 ratio using a simple allocation method to one of two experimental groups: 1) sham or 2) stimulation protocol. Randomization will be double-blinded. An independent operator (trained personnel from the research team) will prepare the tsDCS device parameters for each session, but will not participate in the rest of the assessments. Patients and raters will remain blinded to SCS protocol assigned to each participant throughout the study. During the session, subjects will remain in a calm and relaxing environment. All participants will be scheduled for the same procedures and number of scheduled visits during the eight-week follow-up period. (**Table 2**)

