Visit 0 (Screening). Subjects will be informed about study procedures and given a written informed consent to sign voluntarily before any study procedure is initiated (See Informed consent form attached to this protocol). Then, the clinical staff will evaluate the participant in order to obtain a psychiatric and medical history. The MINI will be used to confirm MDD diagnosis, the MADRS to evaluate depressive symptom severity and the CSSRS for suicidality. The clinical research team will perform a full neurological and physical evaluation, ECG, cardiovascular measurements, laboratory tests, urinalysis, urine drug test, and a blood pregnancy test (if applicable). After eligibility is confirmed, a baseline visit will be scheduled.

Visit 1 (Baseline). After verification of eligibility, subjects will be randomized to an “active” or to a “sham” tsDCS protocol. Treatment allocation will remain double-blinded throughout the study to raters and study physicians. A MADRS, CGI-S, CSSRS, PHQ-9, 4DSQ, BES and MAIA will be completed. BMI, waist and abdominal circumference, vital signs, blood sample and ECG will be obtained. A physical and neurological evaluation will be conducted. Participants will complete the ERT and SST prior and during the SCS protocol. Each participant will receive the assigned SCS protocol.

SCS sessions (1-24): Three tsDCS sessions per week will be scheduled. A CSSRS will be completed before each SCS session. Blood pressure and heart rate will be evaluated prior and after each tsDCS session. AE's will be assessed after each session through open-ended questions.

Full visits 2, 3, 4, and 5: A MADRS, CSSRS, CGI-S, CGI-I, PHQ-9, 4DSQ, BES and MAIA scales will be completed.

Anthropometric measures (Visit 3, 4, 5), vital signs, and ECG (Visit 4) will be obtained. A blood sample (visit 4), urine drug test (Visit 4) and pregnancy test will be performed if applicable (visit 4). A physical and neurological evaluation will be

conducted (Visit 3, 4, and 6). Participants will complete the ERT and SST prior and during the SCS protocol (Visit 4). Each participant will receive the respective tsDCS protocol. AE's will be recorded after each tsDCS session.

Full Visit 6 (Final visit): A MADRS, CSSRS, CGI-S, CGI-I, PHQ-9, 4DSQ, BES and MAIA scales will be completed.

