Early withdrawal. A subject may voluntarily decide to end participation at any point during the study. Clinical investigators may decide to end study participation of any subject if it is in the best interest and/or safety of the subject. If at any point during the study a patient has a MADRS suicide item score > one point higher than their visit 1 (baseline) score for any one week, or a score of > 4; or active suicidal behavior on the C-SSRS; or appears to the investigator to pose a risk of self-harm or harm to others, the patient may be withdrawn from the study. Additionally, patients will be withdrawn from the study (and referred for treatment as clinically indicated) if there is a worsening of symptoms at visit 2 or later, as indicated by a CGI-I score of ≥ 6 or more at any time during the study or a minimal worsening of symptoms at visit 3 or later as indicated by a CGI-I score of ≥ 5 at 2 consecutive visits, starting at visit 2; or a 50% increase over baseline in total MADRS rating and a total MADRS > 28, at visit 3 or later. Patients will also be withdrawn from the study at week 3 or later if they demonstrate a ten-point increase from baseline in MADRS score for two successive weeks starting at visit 2. In addition, all patients will be assessed with the C-SSRS on every tsDCS session to elicit risks of potential suicidality. During study participation, a study related clinical investigator will closely monitor all study participants at each study visit for suicidal or homicidal ideation, plan, or intent using clinical interviews as well as the information obtained from rating scales. Transient suicidal ideation will not result in study discontinuation or referral for inpatient care since this may be common for patients with major depressive disorder. In order to maximize subject safety, if a subject exhibits active suicidal or homicidal ideation during study participation that, in the judgment of a clinical study investigator, cannot be managed on an outpatient basis, he/she will be withdrawn from the study and referred for inpatient psychiatric care. Patients with active suicidal behavior may be removed from the study based on C-SSRS criteria, as noted above. All subjects who discontinue study participation prior to visit 6 will be asked to voluntarily undergo endpoint study procedures, if feasible. Additionally, all study participants will be provided with study physician contact information and instructed to contact their study physician 24 hours/day, 7 days/week in between visits should suicidal or homicidal ideation or any other emergency situation occur. If a participant becomes pregnant during the study, participation will be stopped, and the event will be documented as a serious adverse event. The participant will be referred for appropriate medical treatment and follow up with primary care physician and followed by the study team throughout the pregnancy and the outcome documented as required by the IRB and institutional guidelines. We have successfully followed this protocol in our prior

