
outcome and clinical trials studies. A study physician will work with the patient to arrange admission in the event that it is determined that a study participant needs psychiatric or medical hospitalization.

G. SAMPLE SIZE.

This is an exploratory pilot clinical trial for which up to 60 (including screen fails) participants will be screened in an effort to recruit 20 participants that will receive either sham (n=10) or active treatment (n=10) for 8 weeks. Recruitment efforts will be aimed at a 2 patient/month rate. The exploratory nature of the study precludes a sample size that would enable detection of small but still clinically relevant effects at conventional significance thresholds. However, estimates of effect sizes with confidence intervals will be useful as inputs to larger confirmatory studies if these effects fall in an appropriate range (i.e., at least moderate sample effect sizes of approximately 0.50 standard deviations), even if the conventional significance is not achieved.

H. FEASIBILITY OF RECRUITMENT AND RETENTION

Resources and Infrastructure: The University of Cincinnati (UC) College of Medicine, Department of Psychiatry was founded in 1932 and UC is the 14th largest recipient of NIH funding. Among departments of Psychiatry, UC has one of the largest psychopharmacology research programs in the United States dedicated to depression and bipolar disorder. The faculty has a long-term successful record of sustained research support related to mood, eating, and impulse control disorders and pharmacological treatments.

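### If simple allocation means an independent draw for each patient, the planned 10:10 split is only the expected one; a fixed list of 10 and 10 would avoid an average 2.8% loss in standard error

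*Combined protocol and SAP*

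**What the plan says.** The method of allocation is described once, in D.1.2: "Subjects will be randomized in a 1:1 ratio using a simple allocation method to one of two experimental groups". Section D.2 (Visit 1) adds only that randomization follows verification of eligibility. The document does not mention blocks, strata, a list with fixed arm totals, or how the sequence is generated.

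The planned arm sizes are given three times. The abstract has patients "randomized to receive Active (n=10) or Sham (n=10) tsDCS protocols for 8 weeks in a 1:1 ratio", Section A plans to "randomize 20 adult antidepressant-free MDD patients to active (n=10) or sham (n=10) tsDCS protocols for 8 weeks", and Section G screens up to 60 people "in an effort to recruit 20 participants that will receive either sham (n=10) or active treatment (n=10) for 8 weeks".

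Section G gives no power calculation. It says instead that "estimates of effect sizes with confidence intervals will be useful as inputs to larger confirmatory studies", provided the effects are at least moderate, at about 0.50 SD. Section I makes the primary test a planned contrast between groups of the baseline to week 8 difference in MADRS, with two-sided 0.05 tests and intervals.

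On blinding, D.1.2 says "An independent operator (trained personnel from the research team) will prepare the tsDCS device parameters for each session" and keeps that operator out of the other assessments. D.2 says "Treatment allocation will remain double-blinded throughout the study to raters and study physicians".

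**The concern.** Simple randomization ordinarily means an independent 50:50 draw for each patient. Nothing in that procedure holds the arms at 10 and 10, so the stated arm sizes become an average over possible trials. With 20 patients, chance imbalance is common and cannot be repaired after the event.

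What is at stake is precision. Section G presents effect estimates with confidence intervals as what this pilot can give the next trial, so interval width is the natural measure of cost. Any width lost to unequal arms could be avoided without recruiting anyone else.

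**Working it through.** **Inputs.** N = 20, planned 10 + 10 (abstract, Sections A and G). Two-sided α = 0.05 (Section I). Effect of interest 0.50 SD (Section G), used only for power. The plan states no SD, no power and no dropout rate, so it has no derived figure to reproduce. Assumptions: independent 1:1 assignment, all 20 contribute, equal variance in the arms, and the planned contrast treated as a two-sample comparison of change scores. The standard-error ratio does not depend on the SD.

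**Distribution of the split.** The number in the active arm, n₁, is Binomial(20, 0.5), and n₂ = 20 − n₁. For example, P(10:10) = C(20,10)/2²⁰ = 184,756/1,048,576 = 17.6%.

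**Standard error.** SE = SD × √(1/n₁ + 1/n₂). At 10:10 this is 0.447 SD. The ratio to 10:10 is √[(1/n₁ + 1/n₂)/0.2].

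| Split | Probability (either direction) | Probability of this or worse | SE against 10:10 |
|---|---|---|---|
| 10:10 | 17.6% | 100% | 0 |
| 11:9 | 32.0% | 82.4% | +0.5% |
| 12:8 | 24.0% | 50.3% | +2.1% |
| 13:7 | 14.8% | 26.3% | +4.8% |
| 14:6 | 7.4% | 11.5% | +9.1% |
| 15:5 | 3.0% | 4.1% | +15.5% |

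- Averaged over all splits (20:0 excluded, probability 1.9 × 10⁻⁶), the SE ratio is 1.028.
- The median split is 12:8, at +2.1%.
- In 49.7% of trials (17.6% + 32.0%, before rounding) the split is 11:9 or closer, and the loss is at most 0.5%.

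**Effective sample size.** This is 4n₁n₂/20. Since E[n₁n₂] = 20 × 19/4 = 95, its mean is 4 × 95/20 = 19.0 of 20.

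**Confidence interval.** Half-width = t(0.975, 18) × SE.
- 10:10: 0.940 SD.
- Mean over simple allocation: 0.966 SD.
- 14:6: 1.025 SD.
- For comparison, balanced arms with one outcome lost (10:9, 17 df): 0.969 SD.

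**Power at 0.50 SD** (noncentral t): 18.5% at 10:10, and 17.8% averaged over simple allocation.

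**Predictability of the fixed list.** Someone who knows every earlier assignment and always guesses the arm with more places left expects 10 + 2¹⁹/C(20,10) − 0.5 = 10 + 2.84 − 0.5 = 12.3 correct of 20. Under simple allocation the figure is 10.0.

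**The case against.** **The loss may not exist.** Three places in the document give 10 per arm, and D.1.2 may be a loose description of a list of 10 and 10. This stands: the loss is then zero, and only the wording needs attention. The finding is therefore conditional.

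**It is too small to matter.** Power changes by 0.7 percentage points from a base under 19%, and half-widths of 0.94 and 0.97 SD would probably lead to the same planning decision. The mean is also pulled up by rare splits. All of this stands and sets the severity. The tail remains, with about one trial in nine at 14:6 or worse, and the remedy is cheap.

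**Unpredictability is a virtue of simple allocation.** This is true, and the primary outcome is rater-scored at a single site. But 12.3 guesses assumes full knowledge of past assignments. Patients, raters and study physicians are blinded, and the operator who sets the device takes no part in the assessments.

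**Withdrawal or under-recruitment would unbalance the arms anyway.** Under "Early withdrawal", Section F says "A subject may voluntarily decide to end participation at any point during the study", and a list guarantees 10:10 only if all 20 are randomized. The gain nevertheless persists. With assumed independent loss of 10%, 20% or 30% of outcomes, the mean half-width is 1.035 against 1.006, 1.122 against 1.089, and 1.236 against 1.198 SD (simple against list). If recruitment stopped at 14, it would be 1.215 against 1.178. Each gap is about 3%.

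**Stronger readings.** A reader might infer that D.1.2 contradicts the planned 10 and 10. It does not, because 10 per arm is compatible with simple allocation as a target. A reader might also infer bias or an invalid test. Simple randomization is valid, and chance imbalance in numbers does not bias the comparison. Nor does the text show that concealment is absent: Section J refers to a person holding the blinded information, although it does not say how assignments are released.

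**Conclusion.** The point holds as a minor, conditional efficiency finding. If allocation is independent for each patient, the plan gives up about one patient's worth of precision on average, with a 26.3% chance of 13:7 or worse. The typical loss is smaller than the mean, and often negligible.

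The arithmetic is exact under the assumptions listed. What the document leaves open is which method was meant, so a loss can be stated only for the ordinary meaning of the term.

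**What to change.** In D.1.2, replace the reference to simple allocation with: *a computer-generated, concealed list that is one random permutation of 10 active and 10 sham assignments*. Add that each assignment is released to the device operator only after that patient is enrolled, and that the list is kept from staff who enrol or rate patients. If such a list was already intended, the same words settle the matter.

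The change takes two sentences and a different list, with no added patients, visits or procedures. The real cost is the rise in worst-case predictability, which is why the release step belongs with the change.

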Anthropometric measures, vital signs, blood sample, pregnancy test and ECG will be obtained. A drug urine test will be performed. Participants will complete the ERT and SST prior and during the SCS protocol. Each participant will receive the respective tsDCS protocol. A physical and neurological evaluation will be conducted. AE's will be recorded after each tsDCS session.

Table 2. Schedule of events

Menstrual phase will be documented at each full visit. Participants will be referred for aftercare after study completion with their primary care physician (PCP) or will receive referral information for a psychiatrist or other mental healthcare professional. Participants will be compensated with a total of up to \$250 (\$10 per visit) for their time and effort through a prepaid debit card. Subjects are expected to attend to the Lindner Center of Hope a total of 25 times. Free parking is provided. Additional unscheduled visits may be arranged if needed. Full visits may be scheduled with a window of +/- 4 days. A participant may not be allowed to continue on the study if the participant misses more than 6 consecutive tsDCS sessions or has missed more than 8 tsDCS sessions on separate occasions.

D.3. Participation of human subjects.

This study will be performed in compliance with International Conference of Harmonization (ICH) Good Clinical Practice (GCP) and corresponding local regulations. Participation will be voluntary; subjects will be informed in detail about the

study, including potential risks and benefits of participating and will agree to participate by reading and signing an informed consent (See informed consent form attached to this protocol). The informed consent form will be written in a language that is understandable for potential participants. The study team will be available to answer any questions before the potential participant decides to sign the informed consent form. All required study documentation will be confidential and archived as required by regulatory authorities. *Data and Safety Monitoring Plan:* This plan will include monitoring of efficacy and safety data by an independent Data Safety Monitoring Board (DSMB) that will meet every six months and will provide oversight and monitoring to ensure the safety of participants and the validity and integrity of the data. Detailed information on the Data and Safety Monitoring plan and DSMB is contained in *Protection of Human Subjects* section of this protocol.

E. OUTCOMES

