Primary Outcome: Difference in change from baseline to week 8 (or last available observation) in MADRS scores between active and sham tsDCS groups. **Secondary Outcome:** **a)** differences in AE's frequency between active and sham tsDCS groups, **b)** association between change from baseline to week 8 (or last available observation) in MADRS scores, and clinical (CGI-I, CGI-S, PHQ-9, MAIA, BES and 4DSQ), autonomic (BP, HR) and metabolic (anthropometric, adiponectin, leptin, cortisol, FGF-21 and LCn-3) parameter change from baseline to week 8(or last available observation), and **c)** MADRS sub-component (98) scores, clinical parameters (CGI-I, CGI-S, PHQ-9, MAIA, BES and 4DSQ), autonomic (BP, HR), and metabolic (anthropometric, adiponectin, leptin, cortisol, insulin, FGF-21 and LCn-3) parameters change from baseline to week 8 (or last available observation) difference between Active and Sham tsDCS groups. **Exploratory outcome measures:** **a)** difference in change from baseline to week 8 (or last available observation) in offline ERT and Stop signal task scores between active and sham tsDCS groups; and **b)** difference in change from baseline to week 8 (or last available observation) in offline and online change ERT and stop signal task scores between active and sham tsDCS groups

F. SAFETY MEASURES

Potential Risks. Safety evaluation will consist in recording all laboratory tests, vital signs and ECG results, suicidality monitoring (each SCS session), physical and neurological examinations and any adverse events (AE). As mentioned above, literature suggests that current density below 25 mA/cm² induces no tissue damage (99). Findings will be recorded as AEs at the discretion of the investigator. Known side effects to tsDCS are paresthesia, redness, itch, or pain in stimulated area. If they occur, these side effects tend to disappear within minutes to hours after stimulation. To our knowledge, no serious adverse effects have been reported with the use of transcutaneous direct current stimulation protocols using 2.5mA/cm² (100).

Risk/Benefit Assessment. Participants will be informed that there are other FDA approved treatment alternatives for major depressive disorder and that their participation in this study is voluntary. Therapeutic options include antidepressant medications, psychotherapy, invasive and non-invasive neuromodulation tools. Participants will also be

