Data management and analyses will be organized and performed by the research team under the guidance of [name], Director of the Division of Biostatistics in the Department of Psychiatry at the University of Cincinnati, who has participated in the development of this analytic plan. Data will be collected via Case Report Forms. The research coordinator will be responsible for managing the study flow, maintaining case report forms, and entry data into a password-protected database on REDcap.

Data Analysis. *Specific Aim 1: Prediction 1)* Active tsDCS treatment will result in a greater decrease in depressive symptom severity (MADRS) compared to Sham in adult patients diagnosed with MDD. *Efficacy:* Longitudinal effect of tsDCS will be assessed by comparing change in MADRS scores from baseline to week 8 (or last available observation). To take maximum advantage of intermediate observations while avoiding assumptions about the trajectory of change over time, we will use a repeated-measures ANOVA model (i.e., with time as a categorical variable), and the primary hypothesis test will be a planned contrast of the baseline-week 8 differences between groups. *Prediction 2)* Active tsDCS is safe and well tolerated in adult patients diagnosed with MDD. *Safety:* A similar analysis as used for efficacy data will be performed for laboratory assays, vital signs, anthropometric, clinical, autonomic and metabolic variables. Frequencies of AE's will be compared between groups using comparative analysis. *Specific Aim 2: Prediction 3)* Baseline and change in interoceptive awareness,

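### Missed sessions can end study participation, not just stimulation, with no firm plan to collect week-8 MADRS, so the primary contrast is open to bias

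*Combined protocol and SAP*

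**What the plan says.** **Attendance rule (section D.2, Protocol visits).** A participant can be barred from going on in the study when he or she "misses more than 6 consecutive tsDCS sessions or has missed more than 8 tsDCS sessions on separate occasions". The consequence is leaving the study. The wording is permissive, so someone decides case by case.

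**Follow-up after leaving (section F, Early withdrawal).** "All subjects who discontinue study participation prior to visit 6 will be asked to voluntarily undergo endpoint study procedures, if feasible". The sentence gives no time for these procedures, and section F schedules no further visits for leavers.

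**Primary outcome (section E).** "Difference in change from baseline to week 8 (or last available observation) in MADRS scores between active and sham tsDCS groups".

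**Primary analysis (section I).** A repeated-measures ANOVA with time as a categorical factor is planned, to make use of intermediate visits, and "the primary hypothesis test will be a planned contrast of the baseline-week 8 differences between groups". The same section repeats the last-available-score fallback. It does not say how the fallback and the model work together.

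The documents give no analysis population, expected dropout rate or sensitivity analysis for missing data.

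**The concern.** Attendance happens after randomisation and may depend on how the patient is doing. Section F lists paresthesia, redness, itch and pain as known effects. Section D.1.2 describes active treatment as 20 minutes at 2.5 mA and sham as short pulses at the start and end, so absence through discomfort could plausibly differ by arm. Patients may also stay away because they feel no benefit or because they have recovered early.

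If non-attendance leads to removal, a week-8 score that could have been requested may never be taken, and an earlier score can take its place. MADRS is scheduled only at screening and full visits, not at every session, so the last score may predate the absence that led to removal.

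Section G says the product of this pilot is an effect size with a confidence interval for planning a larger trial. Bias in that estimate is therefore the relevant harm. With 10 patients per arm, each one carries 10% of the arm mean.

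**Working it through.** Section G states no power, SD, expected MADRS difference or dropout rate, so there is no plan figure to reproduce.

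**Step 1: when the rule can apply.** Section D.2: "Three tsDCS sessions per week will be scheduled". Over 8 weeks that is 3 x 8 = 24 sessions, which matches the plan's numbering of sessions 1 to 24.

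- More than 6 consecutive means 7: 7/3 = 2.33 weeks, and 7/24 = 29% of sessions.
- More than 8 separate means 9: 9/24 = 37.5% of sessions, needing at least 9/3 = 3 weeks.

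Removal can therefore come five weeks or more before week 8.

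**Step 2: what then enters the primary analysis.**

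- Endpoint MADRS obtained at calendar week 8: nothing is replaced.
- Endpoint MADRS obtained at exit: the score is earlier than week 8.
- No endpoint MADRS: the last full-visit score is all there is.

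The plan allows all three. If earlier scores are carried forward, the arithmetic below applies. If instead the model is fitted by likelihood to the observed visits, nothing is carried forward, but the week-8 scores are still absent and the result rests on a missing-at-random assumption.

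**Step 3: illustration under carry-forward.** From the plan (section G): 10 per arm and a benchmark of about 0.50 SD. Assumed:

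- SD 8
- mean change at week 8 of -12 active and -8 sham, so a true difference of -4.0 points = 0.50 SD
- linear change over time
- exit at week w = 2.33, 4 or 6, with the score taken at exit
- removed patients otherwise follow their arm's mean course

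With a fraction p removed from an arm whose week-8 change is D, the arm mean becomes (1 - p) x D + p x D x w/8. Its shift is p x |D| x (1 - w/8). Two removals in an arm of 10 give p = 0.2.

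| Exit week | 1 - w/8 | Two active, no sham: shift | Difference becomes | Two sham, no active: shift | Difference becomes |
|---|---|---|---|---|---|
| 2.33 | 0.709 | 0.2 x 12 x 0.709 = 1.70 | -2.30 | 0.2 x 8 x 0.709 = 1.13 | -5.13 |
| 4 | 0.50 | 1.20 | -2.80 | 0.80 | -4.80 |
| 6 | 0.25 | 0.60 | -3.40 | 0.40 | -4.40 |

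The shift is 0.4 to 1.7 points. Divided by 8, that is 0.05 to 0.21 SD, or about 10% to 43% of the 4.0-point benchmark. Its direction depends on which arm loses patients.

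**Step 4: equal removal and the null.**

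- Two removals in each arm: -4.0 becomes -3.4, -3.6 or -3.8 (exit at week 2.33, 4 or 6). This is attenuation only.
- No true difference (-8 in both arms), equal removal: bias 0.
- No true difference, two removals in one arm only: a spurious 1.13, 0.80 or 0.40 points (0.14, 0.10 or 0.05 SD).
- Simulation of 40,000 trials (t-test on carried-forward change, assumed within-patient correlation 0.6, three active and one sham removed at week 4): rejection rate about 5% under the null. With the assumed true effect, power falls from 18.8% to 9.1%.

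**Step 5: set against precision.** The 95% half-width at 10 per arm is 2.101 x sqrt(2/10) = 0.94 SD, or about 7.5 points at SD 8. The shift in Step 3 is about 5% to 23% of that.

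**The case against.** A reader might infer that section F's endpoint procedures take place at the time of leaving, so that week 8 is always replaced. The text gives no timing. If they are done at week 8, nothing is replaced. The schedule of events (Table 2) was not readable in the text reviewed. If it fixes this timing, that part of the point falls away.

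A reader might also infer that carrying the last score forward is settled, that removed patients drop out of the analysis, or that the randomised comparison is broken. The documents support none of these. A repeated-measures model is named alongside the fallback, and nothing excludes removed patients. The rule is discretionary and identical in both arms, and patients and raters are blinded. In the illustration, equal removal creates no false effect.

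Further points on the other side have weight:

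- Someone absent for over two weeks may not come at week 8 either, and the fix can only ask. What it adds is a stated time and the intermediate scores.
- Section D.1.2 lets intensity be lowered in both arms, which narrows the discomfort route without closing it.
- Scores taken after stimulation stops answer a question about assignment rather than about stimulation received, and other care may have begun. That is a choice of target, and an exploratory pilot need not meet a confirmatory standard.
- Section F's withdrawals for worsening feed the same fallback and depend on outcome more directly. The attendance rule is one part of a wider missing-data gap.
- The shift is small beside the confidence interval.

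These limit the size and tone of the point. They do not remove it: the plan still allows an avoidable loss of week-8 scores, and a bias does not show in the width of an interval.

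**Conclusion.** The point holds as an openness to bias, in either direction, that can be reduced cheaply. The plan ties non-attendance to leaving the study, sets no time for the endpoint MADRS, and leaves the fallback and the model unreconciled.

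A shift of 0.05 to 0.21 SD for a two-patient imbalance is modest but not negligible against a 0.50 SD benchmark. It rests entirely on the assumed SD, trajectories, exit times and number removed, and on scores being carried forward. It would be smaller if removed patients would have changed little after exit. It would be larger if no exit score is taken and the last full visit came well before the absence. The calculations show no inflation of false positives in the case simulated. The concern is the accuracy of the effect estimate that section G wants to pass on to a larger trial.

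**What to change.** Leave the session thresholds and all clinical withdrawal criteria as they are, and make three changes.

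1. In section D.2, state that stopping sessions for non-attendance does not end study follow-up. Ask these patients to complete MADRS at the remaining full visits, and at minimum at calendar week 8 counted from baseline. This stays voluntary.
2. In section F, give the time of the endpoint MADRS for anyone who discontinues before visit 6.
3. In sections E and I, state that these scores enter the repeated-measures primary analysis under the randomised arm. Use the last available score only when no week-8 score can be obtained, and say how that is done within the model.

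The cost is a few sentences and some assessment-only visits for a handful of patients. Section D.2 already permits unscheduled visits, and the sample size does not change. The downside is that some scores will be taken after stimulation has stopped and possibly after other treatment has begun. Record the date of the last session and any new treatment so that this can be described.
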